### ***Efficacy data – missing***

To evaluate the impact of missing data and of the earlier handling methods, a number of sensitivity analyses will be performed for the primary endpoint utilizing the primary analysis population (mITT).

- **As treatment multiple imputation:** For any patient with missing values, the estimates for the missing assessments will be based on the actual treatment group of that patient. One-hundred imputations will be performed. A predicted mean matching based on a monotone regression (in case the missing data pattern is monotone) or on a fully conditional specification regression (in case the missing data pattern is arbitrary and non-monotone) will be applied. The predicted mean matching method imputes an observed value which is closest to the predicted value from the simulated regression model for each missing value. It ensures that imputed values are plausible and might be more appropriate than the regression method if the normality assumption is violated. The regression model will condition on observed values of the primary outcome measured at other time points (including baseline measurements) and possible other covariates that are related to the missing data pattern and/or primary endpoint. The statistical model for the primary endpoint will then be applied to each imputed dataset separately. The estimated parameters will be pooled using Rubin’s combining rules. This analysis will be applied under the assumption of data missing at random (MAR).
- **Tipping-point analysis:** The tipping point is defined as the difference in the change from baseline in ALSFRS-R score at week 48 between FAB122 and placebo at which the study conclusion (i.e. the statistical significance) changes. This analysis is done to explore the impact of MNAR data and is therefore a sensitivity analysis under the assumption of MNAR. Missing data are imputed over a range of possible scenarios for treatment effect, in order to identify the scenario (or tipping point) that reverses the study conclusion as obtained in the original MAR/MCAR analysis. To find this tipping point a systematic shift will be applied to the (as-treated) imputed values (i.e. a MNAR adjustments in the multiple imputation process) in the FAB122 treatment arm. These shifts will cover a large enough range, in steps of 0.2 to find the value for which the analysis shows a change in significance of the primary hypothesis test, the tipping point. For each shift the primary analysis method will be repeated on the 20 multiple imputed data sets. In case such a tipping point has an unrealistic value (as per clinical decision), this will support the treatment effect found in the primary analysis.

---

 All deaths (including unrelated) are meant here, as it is safe to assume all deaths are related to ALS. In case of unrelated deaths, this will be very small number.

- **Hybrid approach:** With the hybrid approach the missing weeks for patients who discontinued due to AE or lack of efficacy will be imputed using the placebo-based pattern imputation under the MNAR assumption and under the assumption of monotone missing data. All other discontinuation/missing will be imputed using multiple imputation by treatment group using a multivariate stepwise approach using a fully conditional specification (FCS) regression method (Rubin, 1987), assuming the missing data pattern is arbitrary and non-monotone. Missing baseline values, if any, will be imputed using age and time since diagnose. Subsequent visits will be imputed using data of all previous weeks in a stepwise fashion. Twenty imputations will be performed.
- **Completer analysis:** This analysis includes only patients who have completed the study up to week 48, and those patients who died prior to 48 weeks assuming they would otherwise have completed the study up to 48 weeks.
- **Per Protocol and ITT Analysis:** This analysis will include patients from the PP and the ITT analysis sets. The same missing data imputation and ICE strategy as for the mITT analysis will be applied to these sensitivity analyses.

For presentation of descriptive statistics of efficacy data, no imputation or sensitivity analysis will be included, and data will be presented ‘as is’. All these analyses will be done on data available at the visit considered. In summary tables, the number of patients without missing data will be presented (per visit, if applicable) unless otherwise specified. In calculations of percentages, the denominator will be the number of patients in the applicable analysis population.

### ***Safety data***

Using the most conservative approach, missing/incomplete information related to AEs will be handled as listed below, to indicate an AE as being treatment emergent or presented having a certain intensity/causality. Note that imputed dates/times or intensity/causality will not appear in data listings, but only in descriptive statistics tables (where applicable).

- In case of (partially) missing onset dates, the AE will be handled as follows:
  - If full start date is available, and on or after first dosing date, the AE is considered treatment emergent.
  - In case full stop date is available and prior to first dosing date, the AE is considered prior.
  - If the day part of the start date is missing:
    - The AE is considered treatment emergent if the month and year of the start date are the same or after the month and the year of the first dosing date.
  - If the day and month part of the start date are missing:
    - The AE is considered treatment emergent if the year of the start date is the same or after the year of the first dosing date.
  - In case the start date is completely missing:
    - If stop date is fully available and on/after the first dosing date, the AE is considered treatment emergent.
    - If the stop date is partially missing, but the month and year (or year alone in case of missing month) are after the month and year (or year alone) of the first dosing date, the AE is considered treatment emergent.
  - In case full start date and full stop date are missing, the AE is considered treatment emergent.

- In case intensity is missing for a certain TEAE, it will be regarded as severe.
- In case causality is missing for a certain TEAE, it will be regarded as related.
- In case seriousness is missing for a certain AE, then this is discussed and addressed prior to database lock and unblinding in agreement with the sponsor and the Data Management vendor.

Regarding prior/concomitant medication, a similar approach will be followed for partially missing dates, as will be done for AEs as described above.

Using the most conservation approach, missing/incomplete information regarding medical history/ALS history will be handled as follows to calculate the duration of symptom onset:

- If only the day part of the date of diagnosis is missing, then the first of the month is imputed for the start date.
- If the day and month part of the date of diagnosis is missing, then 01 January is imputed for the start date.

If the complete date is missing, then no imputation can be performed, and this will need to be discussed and addressed prior to database lock and unblinding in agreement with the sponsor and the Data Management vendor.

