## **6.1. Screening and Eligibility Assessment**

Subjects will report to the clinical site for a screening examination between Day -12 and Day -2.

Prior to performing any study-related activities or evaluations, the patient must be thoroughly informed about all aspects of the study, including scheduled visits and activities. Patients will sign the study-specific consent form prior to any screening procedure. A signed copy of the informed consent form (ICF) should be provided to each consenting subject and with the original to be retained in the subject's study records. Depending on local regulations an independent ICF for Future Biomedical Research (FBR) should also be signed.

The following information and procedures will be performed and documented as part of the screening assessment:

- Assessment of eligibility according to inclusion/exclusion criteria
- Demographics, including sex, ethnic origin, date of birth
- Medical history including query for baseline signs/symptoms
- Review of prior and ongoing concomitant medications (taken in previous 30 days)
- Complete physical examination
- Neurological examination
- Height, weight and calculated BMI
- Vital signs measured with the subject in a supine/semi-supine position (for at least 5 minutes prior), including blood pressure, pulse rate, pulse oximetry and temperature

---

- Standard 12-lead ECG (subject should be in a supine/semi-supine position for at least 5 minutes prior to assessment)
- Nerve Conduction Study (NCS)
- Fasting blood samples for routine clinical labs (clinical chemistry, haematology). See table 2 for lab assessments.
- Blood samples for serology (HIV, and hepatitis B and C evaluations)
- Urine samples for urinalysis
- $\beta$ -hCG in plasma and urine pregnancy test only in women of childbearing potential
- ALS evaluation procedures: ALSFRS-R and Slow Vital Capacity (SVC)
- Plasma vitamin B6 levels, and, if necessary, vitamin B6 supplements (pyridoxine (100 mg/day)) will be prescribed

Compliance with inclusion criteria and exclusion criteria will be verified against information collected and documented in the database.

Once all inclusion criteria are met, exclusion criteria ruled out, and safety\* laboratory measurements obtained and reviewed, consenting subjects are eligible for randomization into the study.

\*Vit B6 is not considered a safety assessment at screening

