## 9. SAFETY REPORTING

Adverse events will be recorded (using MEDRA version 24.0) beginning immediately after the ICF is signed. The investigator (and/or designee) must document all AEs reported by the subject from the signing of the ICF through completion of the final follow-up. Any subject who is withdrawn from the study due to an AE shall be followed until the outcome of the event is determined, and the investigator will document available follow-up information on the subject's database.

In this study, an external Data Safety Monitoring Board (DSMB) will be appointed to review all safety data generated during the study. For more details see section 13.2.1

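### SAP 5.2 leaves an adverse event with no start date and a partial stop date in the first-dose month (or year) unclassified, contrary to its own conservative principle

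*SAP*

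**What the plan says.** The principle heading the AE list in SAP 5.2 (Safety data) is "Using the most conservative approach, missing/incomplete information related to AEs will be handled as listed below, to indicate an AE as being treatment emergent". The bullets that bear on this point are:

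- Start date lacking only the day: "The AE is considered treatment emergent if the month and year of the start date are the same or after the month and the year", compared with first dosing.
- Start date lacking day and month: "The AE is considered treatment emergent if the year of the start date is the same or after the year of the first dosing date".
- Start completely missing, stop complete: "If stop date is fully available and on/after the first dosing date, the AE is considered treatment emergent".
- Start completely missing, stop partial: "If the stop date is partially missing, but the month and year (or year alone in case of missing month) are after the month and", again compared with first dosing.
- Last bullet: "In case full start date and full stop date are missing, the AE is considered treatment emergent".

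The only bullet that assigns an event to the pre-dose period requires a complete stop date before first dose. SAP 5.7.1 sends incomplete dates back to 5.2 and offers no default of its own. It builds the tables by system organ class, severity, relationship, discontinuation, seriousness and special interest from treatment-emergent events.

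**The concern.** Four of the five bullets count the boundary period, or the complete absence of dates, as treatment emergent. The partial-stop bullet alone uses a strict *after*. The effect runs backwards: an event with no date information is counted, while one known to have ended in the first-dose month meets no condition.

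At stake is completeness of the safety tables. For month-level dates, the affected events ended close to first dose. Protocol 9.1.4 makes any AE suggesting neuropathy an event of special interest, and the special-interest table is also built from treatment-emergent events. No efficacy analysis or confirmatory test is touched.

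**Working it through.** There is no figure in the plan to reproduce. The check applies the rules to test cases and then sizes the gap under stated assumptions.

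**Test cases.** Take first dose on 10 March 2022 (an illustrative date) and a completely missing start date.

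| Stop date recorded | Rule as written | With *the same as or after* |
|---|---|---|
| 20 Mar 2022 | treatment emergent | treatment emergent |
| Mar 2022 | no condition met | treatment emergent |
| Apr 2022 | treatment emergent | treatment emergent |
| 2022 | no condition met | treatment emergent |
| 2023 | treatment emergent | treatment emergent |
| none | treatment emergent | treatment emergent |
| 5 Mar 2022 | prior | prior |
| Feb 2022 | no condition met | no condition met |

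The last row is harmless, because the event plainly ended before dosing. The gap is in the second and fourth rows.

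**When did the affected events end?** AE recording starts "beginning immediately after the ICF is signed" (Protocol 9), and "Subjects will report to the clinical site for a screening examination between Day -12 and Day -2" (Protocol 6.1). Assume consent at the screening visit, so at most 12 pre-dose days of collection, and a stop date uniform over the possible days. The chance that the event stopped on or after first dose is A / (A + B). A is the number of days from first dose to the end of the month or year, and B is the number of pre-dose collection days.

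- Year only, first dose 1 July: 184 / (184 + 12) = 94%.
- Year only, first dose 1 December: 31 / (31 + 12) = 72%.
- Month known, first dose on day 15 of a 30-day month: 16 / (16 + 12) = 57%.

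With screening on Day -2, B = 2 and the same cases give 184/186 = 99%, 31/33 = 94% and 16/18 = 89%. The 12-day figures are therefore the low end of the screening window.

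All of these concern the end of the event. An event that ended before first dose must have begun before it, but one that ended after first dose may have begun during screening. So each percentage is at most an upper bound on the share with onset after first dose.

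**How many post-dose stops does the rule miss?** Consider only events with no start date and a partial stop date. Count every first-dose day in a 365-day year against every stop day from first dose to Day 336 (337 days) or Day 504 (505 days), all equally likely.

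- Month known: stops in the first-dose month total 7×496 + 4×465 + 406 = 5,738, where each term is n(n+1)/2 for a month of n days. Missed: 5,738 / (365×337) = 4.7% over 48 weeks; 5,738 / (365×505) = 3.1% over 72 weeks.
- Year only, 48 weeks: (28×337 + 337×338/2) / (365×337) = 66,389 / 123,005 = 54%.
- Year only, 72 weeks: (365×366/2) / (365×505) = 66,795 / 184,325 = 36%.

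With *the same as or after*, each becomes 0%.

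**What does the change over-include?** Take stops in the 12 days before first dose, 365×12 = 4,380 combinations. Those in the first-dose month number 12×78 + 12×(365 − 12×13) = 3,444, or 79%. Those in the first-dose year number 78 + 12×(365 − 13) = 4,302, or 98%. These would also be counted as treatment emergent.

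**The case against.** The strongest objection is that a reader might infer the SAP declares these events not treatment emergent. It does not. No bullet says so, and the pre-dose bullet needs a complete stop date. The conservative heading could be used to resolve an unclassified event in favour of inclusion. The last bullet, read as meaning that no complete date is available, would bring the events in. This stands in part: the correct description is *unclassified*. But that reading of the last bullet would make the partial-stop bullet redundant, and it would count events that clearly ended in an earlier month. The natural reading is that both dates are wholly absent. A programmer who assigns the flag only when a listed condition is met would leave these events out.

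Three further inferences are tempting and not supported:

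- **That the events would survive only in listings.** The overview table in SAP 5.7.1 has a row for any serious AE, separate from the serious treatment-emergent row, so a serious event would still be counted there.
- **That most of the affected events are true treatment-emergent events.** Under Protocol 9.1.1 emergence turns on onset or worsening after first dose. The percentages describe when the event stopped.
- **That medication has the same gap.** SAP 5.2 promises a similar approach for medication dates, but SAP 5.7.5 treats a medication as concomitant unless it both started and stopped before first dose. No loss is shown there.

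It is also fair that the trigger is rare. Protocol 9.5 asks for an onset date for every AE, events are asked about at visits and calls, and Protocol 12.3 provides for data queries. The rule is the same in both arms.

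**Conclusion.** The point holds as a minor fault in one rule. An AE with a completely missing start date and a partial stop date in the first-dose month, or in the first-dose year when only the year is known, meets no treatment-emergent condition in SAP 5.2. Read naturally, it would be omitted from the treatment-emergent tables, which conflicts with the section's stated principle and with its parallel bullets. The missed shares of 3.1% to 4.7% (month known) and 36% to 54% (year only) apply only to events with this date pattern that ended after first dose, and they rest on uniform dates. They are not shares of all AEs. The documents give no count of such events. It is likely very small, and so is the effect on the tables.

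**What to change.** Two edits to the AE list in SAP 5.2, before database lock and unblinding:

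1. In the partial-stop bullet, replace *are after* with *are the same as or after*.
2. In the last bullet, say that both the start date and the stop date are *completely missing*, so that it cannot be read as covering partial dates.

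The cost is a few words and the matching line of code. A few events that ended during screening may then be counted as treatment emergent, which the SAP's conservative principle already accepts for partial start dates. No change to the medication rule is needed.

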### ***Other***

Based on the BDRM, certain values can be decided to be excluded from analyses. These values will be listed, but not included in descriptive statistics, plots or statistical analyses. This may be (outlier) data that are a result of unambiguous measurement errors.

### **5.3 Mapping of unscheduled or early termination visits**

When visit assessments are missing, repeat assessments performed within the agreed time window of +/- 7 days will be mapped to the appropriate visit in the database by the DM vendor. Repeat assessments performed outside of these agreed time windows are collected in the database using an unscheduled visit. For these unscheduled assessments following a missing protocol visit, mapping will be done to the (closest) protocol visit at which the applicable assessment should have been performed before the date of unscheduled visit.

In case of a repeated or additional assessments for non-missing assessments, mapping will only be done for replacement if this is clearly agreed (at patient and visit level) with the client and specified by DM vendor (e.g. because it replaces an erroneous measure collected at the actual visit), and as such will be used in statistical data presentations. These agreements will be documented during the BDRM.

For patients that withdraw early from the trial, an early termination visit is scheduled 7-14 days after withdrawal, for which the same procedures as for visit 8 will be performed. The data of this early withdrawal will be mapped to the most appropriate scheduled post-baseline visit as applicable per assessment, to be agreed together with the DM vendor and the client on occurrence. The documentation of these agreements is to be finalized during the BDRM. For early termination visits in general mapping will be done to the closest protocol visit at which the applicable assessment should be performed after the date of early termination.

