#### **3.3 Blind Data Review Meeting**

The patients will be classified during the (Blinded) Data Review Meeting (BDRM) to the analysis populations using the protocol deviations. Invitees to this meeting are the Sponsor Medical Representative (CTL or delegate), the Sponsor Project Manager (PM), the Sponsor PK scientist, Julius Clinical PM, Julius Clinical Data Manager (DM) and the Certara lead statistician, but more roles can be invited if considered necessary. Input to this meeting will be supplied by the involved Data Management Department or the responsible PM at least one week in advance of the meeting: a blinded list of all protocol deviations (including missing and outlier data), with specific detailing and description regarding the deviation, preferably in excel.

This meeting will be held in a blinded manner. The goal of this meeting is to reach consensus on minor and major protocol deviations. In case of a major deviation impacting the primary or secondary endpoints, the specific patient will be excluded from the PP population, either completely or from a specific time point onwards. The meeting must be held prior to database lock and unblinding.

The decisions taken during this meeting will be documented by the PM (or a delegate as agreed) and sent for review to all parties involved as soon as possible after the meeting, but before database lock. If all parties involved agree, then the document is finalized, signed and stored before database lock by the PM.

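### SAP 5.3 by default moves early-termination data forward and unscheduled data back with no maximum distance, so some secondary measures can be analysed almost 12 or 24 weeks from their true date

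*SAP*

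**What the plan says.** SAP 5.3 has three mapping rules.

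- **Repeats of a missing assessment:** "repeat assessments performed within the agreed time window of +/- 7 days will be mapped to the appropriate visit".
- **Unscheduled assessments outside that window:** "mapping will be done to the (closest) protocol visit at which the applicable assessment should have been performed before the date of unscheduled visit". This rule needs a missed visit first.
- **Early-termination visits:** "an early termination visit is scheduled 7-14 days after withdrawal". The data are "mapped to the most appropriate scheduled post-baseline visit as applicable per assessment, to be agreed together with the DM vendor"; the sponsor side is a party to that agreement too. The same paragraph then gives a default: "in general mapping will be done to the closest protocol visit at which the applicable assessment should be performed after the date of early termination".

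On the individual agreements for early-termination visits, SAP 5.3 adds: "The documentation of these agreements is to be finalized during the BDRM". Of that review meeting, SAP 3.3 says: "The meeting must be held prior to database lock and unblinding".

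SAP 5.6.2 analyses SVC, the HHD mega score, the ALSAQ-40 total and the VAS with a model like the primary one. EQ-5D-5L, staging and ECAS are tabulated by visit. It applies no imputation to these endpoints.

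**The concern.** The direction of mapping depends on how a visit is labelled, not on when the assessment was made. Suppose a patient misses week 24 and completes the ALSAQ-40 ten days later. Labelled unscheduled, the score is a week-24 value. Labelled early termination, it is by default a week-48 value.

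The mapped value enters the analysis as observed data. For the secondary measures it takes the place of a value that would otherwise be missing. ALS patients decline over time, so moving a score forward makes the later visit look too good, and moving one back makes the earlier visit look too bad. Patients who leave the trial include those who reach the respiratory-insufficiency criteria (Protocol 6.5), so the affected patients are not a random sample.

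The case-by-case provision gives no criterion for choosing a visit. The mapping therefore cannot be reproduced from the SAP alone.

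**Working it through.** **Design figure (Protocol 11.2).** Difference 3.0, SD 7.5, allocation 2:1, 90% power, two-sided 5%. Placebo n = 1.5 × (1.960 + 1.282)² × (7.5/3.0)² = 98.5, rounded up to 99. With 198 active that is 297, against 300 stated. Power at 200 and 100 is 0.904. The design figure reproduces. The standard error of the difference is 7.5 × √(1/200 + 1/100) = 0.92 points, used below as a yardstick.

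**Largest shift.** Both defaults refer to visits at which the particular assessment is due, so the bound is the longest gap between consecutive due visits (Protocol 8.1.1 and 8.1.3 to 8.1.7). The maximum is gap × 7 − 1 days, or gap × 7 − 8 days if the ±7-day rule is applied first.

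| Assessment | Longest gap | Maximum shift | After the ±7-day rule |
|---|---|---|---|
| ALSFRS-R to week 48 (clinic and telephone) | 4 weeks | 27 days | 20 days |
| ALSFRS-R after week 48 | 12 weeks | 83 days | 76 days |
| SVC, HHD, EQ-5D-5L/VAS, staging | 12 weeks | 83 days | 76 days |
| ALSAQ-40, ECAS | 24 weeks | 167 days | 160 days |

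This takes the date of early termination to be the date of the visit. If it means the withdrawal date, the visit falls 7 to 14 days later and the forward maxima shrink by that much: 167 − 7 = 160 to 167 − 14 = 153 days for ALSAQ-40 and ECAS.

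**Effect of the label.** Week 24 is day 168 and week 48 is day 336 (SAP 2.5). An ALSAQ-40 on day 178 is 10 days from week 24 if unscheduled, and 336 − 178 = 158 days from week 48 if early termination.

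**Size in ALSFRS-R points.** Protocol 11.2 takes placebo decline as 12 points in 12 months, or 12/52 per week.

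- To week 48: 4 × 12/52 = 0.92 points at most per mapped patient.
- After week 48: 12 × 12/52 = 2.77 points at most.

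**Primary endpoint.** Under the default, only early-termination scores taken between weeks 44 and 48 become week-48 values. The documents give no count, so assume 2% to 10% of one arm. The arm mean then moves by at most 0.02 × 0.92 = 0.02 to 0.10 × 0.92 = 0.09 points. The upper figure is about a tenth of the 0.92 standard error, against a design effect of 3.0.

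If telephone calls did not count as protocol visits for mapping, the gap would be 12 weeks and the range 0.02 × 2.77 = 0.06 to 0.10 × 2.77 = 0.28 points.

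**Carry-back at the end of follow-up.** A later due visit normally bounds carry-back. Protocol Table 1, footnote 1, ends the study at week 48 for about two-thirds of patients. If such a patient misses week 48, nothing in SAP 5.3 limits how late an assessment may be and still count as week 48. At the planning rate each month of delay adds about 1 point of apparent decline.

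**The case against.** Much of the case on the other side stands.

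- A reader might infer that early-termination data always go forward. They do not. The forward rule holds only in general, and the paragraph provides for individual decisions settled at a blinded meeting before database lock. That guards against choices driven by treatment. It does not supply a criterion.
- A reader might infer that carry-back has no limit at all. It requires a missed visit, and the next due visit normally bounds it. The open-ended case is after a patient's last planned visit.
- A reader might carry the 12- and 24-week figures over to the primary endpoint. Telephone visits collect ALSFRS-R every 4 weeks, so they do not apply there.
- The rule may look like last observation carried forward. It fills only the next due visit. A patient leaving just after week 24 has ALSFRS-R placed at week 28, and week 48 stays missing.
- Forward mapping avoids a clash when the earlier visit already has a value. That is a fair reason for it, but listing the extra value also resolves the clash.
- The endpoints with large shifts lie outside the test hierarchy, and SAP 5.6 calls them explorative. This limits the consequence but does not make the dating correct.

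It is also tempting to say that the rule favours FAB122. Protocol 11.4 expects discontinuation of 7% against 3% for adverse events and 10% against 5% for lack of efficacy, which sum to 17% against 8%. Those are treatment discontinuations. The early-termination rule covers withdrawal from the trial, and patients who stop treatment may stay in follow-up. The documents give no trial-withdrawal rates by arm, and forward and backward mapping err in opposite directions.

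**Conclusion.** The concern holds for the secondary endpoints. Followed as written, the two defaults can date a value just under 12 weeks wrong for SVC, HHD, EQ-5D-5L/VAS, staging and late ALSFRS-R, and just under 24 weeks wrong for ALSAQ-40 and ECAS. These are maxima; the number of patients affected is unknown.

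For the primary endpoint the effect is small: at most 0.92 points in an affected patient, and 0.02 to 0.09 on an arm mean if 2% to 10% are mapped. That rests on telephone visits counting for mapping, on an assumed share, and on average placebo decline, which may be too slow for patients who withdraw. The primary conclusion is unlikely to turn on it. The direction of any bias between arms is not established.

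This should be corrected before database lock, mainly for the secondary results and for reproducibility.

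**What to change.** Replace both defaults in SAP 5.3 with one rule based on the assessment date:

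- Map to the nearest visit at which the assessment is due, in either direction, within a fixed window. For example: ±14 days for ALSFRS-R to week 48, ±4 weeks for 12-weekly measures (including ALSFRS-R after week 48) and ±6 weeks for 24-weekly measures. For the 12- and 24-weekly measures the window must be shorter than half the interval (6 and 12 weeks); otherwise it would exclude nothing between visits.
- If that visit already has an observed value, keep it and list the extra one.
- Outside the window, list the value and leave the visit missing. The primary endpoint and CAFS then use their planned imputation. The other secondary endpoints have none under SAP 5.6.2 and stay missing.
- Apply the same cap to carry-back to week 48.
- State that telephone visits count as protocol visits for ALSFRS-R mapping.

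With these windows the largest ALSFRS-R error to week 48 falls to 2 × 12/52 = 0.46 points per patient. The cost is a SAP paragraph, some programming and a few more missing secondary-endpoint visit values. No new data are needed.
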